7.2.3.1 Model checking procedures

7.2.3.2 Graphical presentation of results

The mean and SD estimate from the model mentioned in section 7.2.3 will be displayed graphically. The arithmetic mean (\pm SD) or box plot of change from baseline in PhGA in VAS and PGA in VAS up to Week 29 will be plotted over time by treatment group. The individual plots for raw VAS scores over time will also be presented by treatment. Kaplan Meier plot for time to first moderate, time to first severe and time to first moderate or severe flare will be provided by treatment.

7.3 Exploratory objectives

7.3.1 Variables

7.3.2 Descriptive analyses

7.3.3 Statistical model

7.3.4 Model checking procedures

Refer to [section 7.2.3.1](#).

7.3.5 Graphical presentation of results

The mean and SD estimate from the model mentioned in section 7.3.3 will be displayed graphically. Boxplots for change and percentage change from baseline may be provided for some of the exploratory endpoints. Kaplan Meier plot for time to achieve LLDAS will be provided by treatment. Arithmetic mean (SD) of CD40 concentration-time profiles will be provided by treatment. Scatter plot of B cell subsets (on the Y-axis logarithmic scale) by SRI-4 and sustained corticosteroid reduction response status (X-axis) will be provided by treatment at Week 29, Week 53 (EoT), Week 69 and EoS.

8 Statistical methods for safety and tolerability data

All patients within the Safety analysis set will be included in the safety data analysis. For all safety analyses, Visit 190 (Week 29) will be included in P2 (as per protocol open label dosing starts from Week 29); the “Post-treatment Follow-up” epoch will be summarized together with P2.

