Tuberculosis test ⁷	X																		X	
Pregnancy test ⁵	X	X		X	X	X	X	X	X	X	X	X	X	X	X	X	X		X	
Hematology ⁷	X	X		X	X	X	X	X	X	X	X	X	X	X	X	X	X		X	
Clinical Chemistry ⁷	X	X		X	X	X	X	X	X	X	X	X	X	X	X	X	X		X	
CCI																				
Coagulation Panel ⁷	X	X ⁶					X ⁶				X ⁶								X ⁶	
Autoantibodies ⁷	X	X					X				X				X				X	
CCI																				
IMI blood sample ^{7, 16}		X			X					X										
IMI urine sample ^{7, 16}		X			X					X										
CCI																				
Steroid taper ¹¹					X	X	X	X												
PK Cohort 1 ¹²			X	X	X	X	X	X	X	X	X	X	X	X	X	X	X	X	X	
PK Cohort 2 ¹²			X ¹³	X	X ¹³	X	X ¹³	X	X	X	X ¹³	X	X ¹³	X	X ¹³	X	X ¹³		X	
Immunogenicity ^{12, 14}		X		X			X				X	X			X				X	
CCI																				

Epoch	Screening		Treatment																EoT
Visit Name	Screen	Base-line ²	Treatment – blinded period								Treatment – open label period								EoT
Visit Numbers ¹	1	20	110	120	130	140	150	160	170	180	190	200	210	220	230	240	250	260	299
Days	-28 ±2	-1 to 1	1	15 ±2	29 ±2	57 ±2	85 ±2	113 ±2	141 ±2	169 ±3	197 ±3	211 ±2	225 ±3	253 ±3	281 ±3	309 ±3	337 ±4	340 ±1	365 ±5
Weeks	-4	-1 to 1	1	3	5	9	13	17	21	25	29	31	33	37	41	45	49	49	53
Months	-1	-1 to 1	1	1	2	3	4	5	6	7	8	8	9	10	11	12	13	13	14

IRT	X	X ²³		X	X	X	X	X	X	X	X	X	X	X	X	X	X		X
Dose administration ²¹			X ²²	X ⁶	X	X	X	X	X	X	X ²²	X ⁶	X	X	X	X	X		

Adverse Events	As required																		
Concomitant Treatment	As required																		
Comments	As required																		

^X Assessment to be recorded in the clinical database, EoT – End of Treatment

¹ Visit structure given for internal programming purpose only

² Baseline visit may be combined with Visit 110 at Day 1

³ Body Weight, Height (screening only), Temperature, Blood Pressure, Pulse Rate

⁴ Only for Cohort 1 (VAY736); i.v. CS to be applied approximately 1 hour before first dose

⁵ Pregnancy test on Visit 1 (Screening) in serum, all other visits in urine, only females

CCI

⁷ Central Lab

CCI

¹¹ Corticosteroids should be tapered down to 5 mg/day or lower

¹² Samples are collected pre-dose unless otherwise stated

¹³ Cohort 2 (CFZ533): take one PK sample at pre-dose and another sample 90 min AFTER THE START of i.v. infusion

¹⁴ Cohort 1 (VAY736): serum Cohort 2 (CFZ533): plasma

CCI

¹⁶ Only selected sites

CCI

²¹ Dosing must be done after all assessments are completed, except for PK blood sampling in Cohort 2 (CFZ533) at visits V110, 130, 150, 190, 210, 230 and 250 where pre and post dose blood sampling is required

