On the baseline visit Day 1, following patient eligibility confirmation and completion of all assessments, first dose of study drug/placebo will be administered. The last treatment in the blinded treatment period will be given at the Week 25 visit. The readout for the blinded treatment period will be performed at Week 29. Study drug will be administered every 4 weeks. Unless otherwise stated, all assessments must be completed BEFORE the next dose of study drug is administered.

Guided corticosteroid (CS) reduction

- Patients entering the study on a stable CS regimen are required to undergo a guided CS taper from baseline levels starting at Week 5 in order to achieve by Week 17:
 - a daily CS dose of ≤ 5 mg/day prednisone or equivalent,
 - or a CS dose that is less than the baseline dose, whichever is the lower dose.
- In addition, the patient should remain at the lowered CS dose achieved at Week 17 through to Week 29.
- Patients entering the study without background CS therapy should remain free of any CS regimen or increase in SoC DMARDs through to week 29.

- Patients exceeding the rescue therapy allowances may continue in trial but will be labeled a non-responder for primary endpoint.
- During the open label phase, further reductions in patients' SoC CS and DMARDs may be made on an individual basis as deemed appropriate by the investigator.

Open-label treatment phase

At the end of the Week 29 visit, after all assessments have been performed, the first open label treatment will be administered. Patients in Cohort 1 will receive VAY736 and patients in Cohort 2 will receive CFZ533. Study drug will be administered every 4 weeks. The last treatment will be given at the Week 49 visit, and the End-of-Treatment (EoT) visit will be performed 4 weeks thereafter, at Week 53.

Follow-Up period

After completion of the open-label treatment period, all patients will enter a Follow-Up period in order to monitor safety and efficacy up to Week 69. The Week 69 visit is the End of Study (EoS) visit for patients in Cohort 2 (CFZ533). The study duration for patients in Cohort 2 will be approximately 18 months.

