For Cohort 1 (VAY736). Patients who do not achieve B-cell recovery by Week 69 Visit will enter a Secondary Follow-Up period until achieving B cell recovery criteria (B-cell count is at ≥ 50 cells/ μ L or at least 80% of baseline levels). Safety follow-up visits will be scheduled as deemed appropriate until the patient achieves the B cell recovery criteria, followed by an EoS 4 weeks later.

As per protocol amendment 5 and applicable only for the 3 last patients (see [Figure 1-1](#)): Patients who do not achieve B cell recovery by Week 69 Visit will enter into a Secondary Follow-Up period up to 2 years after EoT or until they achieve B cell recovery criteria (B cell count is at ≥ 50 cells/ μ L or at least 80% of baseline level), whichever occurs earlier.

Safety follow-up visits will be scheduled as deemed appropriate until the patient reaches the 2 years after EoT, with or without achieving the B cell recovery criteria, followed by an EoS as soon as practically possible but no more than approximately 4 weeks later.

2 First interpretable results (FIR)

CCI

3 Interim analyses

CCI

4 Statistical methods: Analysis sets

For all analysis sets, subjects will be analyzed according to the study treatment(s) received.

All patients who received at least one dose of any study drug will be included in the safety analysis set.

The PK analysis set will include all patients with at least one available valid (i.e., not flagged for exclusion) PK concentration measurement, who received any study drug and experienced no protocol deviations with relevant impact on PK data.

All patients with evaluable PD parameter data and no major protocol deviations impacting PD data will be included in the PD data analysis “PD population”.

The analysis sets and protocol deviation codes are related as follows:

Table 4-1 Protocol deviation codes and analysis sets

5 Statistical methods: group presentations

The analyses will be performed on Cohort 1 and Cohort 2 separately unless otherwise specified.

For the analysis plan here onwards, treatment groups are defined as below and these groups will be followed for most summary tables by period and treatment group, unless otherwise stated.

- Blinded period (P1, up to and including Visit 190)

Treatment group for blinded period:

- VAY736
- VAY736 Placebo
- CFZ533
- CFZ533 Placebo
- Open label period (P2, from Visit 190 onwards up to EoT) and
- Post-treatment follow-up (P3, starting day after EoT and ends prior to EoS)
- EoS assessment

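### SAP section 8 files the scheduled Week 29 safety assessments under the open-label period, although they are taken before the first open-label dose

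*SAP*

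**What the plan says.** SAP section 5 defines the analysis periods. The blinded period is "Blinded period (P1, up to and including Visit 190") and the open-label period is "Open label period (P2, from Visit 190 onwards up to EoT"). Visit 190 is the Week 29 visit, so it falls in both. Section 5 applies these definitions to most summary tables unless something else is stated.

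SAP section 8 states something else for safety: "For all safety analyses, Visit 190 (Week 29) will be included in P2 (as per protocol open label dosing starts from Week 29"). The reason given is that open-label dosing starts at Week 29.

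SAP section 1.4 gives the order of events at that visit: "At the end of the Week 29 visit, after all assessments have been performed, the first open label treatment will be administered". Protocol section 3 says the same. Footnote 21 to protocol Table 8-1 reads "Dosing must be done after all assessments are completed, except for PK blood sampling in Cohort 2 (CFZ533") and then lists the visits with pre- and post-dose PK samples. No safety assessment is exempted.

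For groups after Week 29, SAP section 5 uses treatment sequences such as VAY736 Placebo/VAY736, defined for people who take part in the extension.

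**The concern.** The reason given for the rule does not support it. Open-label dosing does start on the day of the Week 29 visit, but it is the last event of that visit. The scheduled safety measurements before it are the end-of-treatment readings of the randomised, placebo-controlled period.

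Two things are at stake. First, safety and immunogenicity are secondary objectives, and the blinded period is the only part of the study with a concurrent placebo group. Its safety tables would stop before the reading that follows the longest blinded exposure. Second, an abnormality first recorded before dosing at Week 29 in a placebo patient would enter that patient's active-drug period, although no active drug had been given.

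**Working it through.** The plan gives no figure to reproduce. The check compares the period rule with the dosing order and then counts visits in protocol Table 8-1.

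**Step 1: order at Week 29.** SAP section 1.4, protocol section 3 and Table 8-1 footnote 21 agree: assessments first, dose last, with Cohort 2 PK sampling as the only exception. Scheduled Week 29 vital signs, ECG, laboratory and ADA results are therefore pre-dose. Some Week 29 data are post-dose: protocol section 4.5.1 keeps Cohort 1 patients at the clinic for at least 2 hours after the Week 29 dose, and reactions seen then follow open-label drug.

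**Step 2: what the blinded period (P1) loses.** Inputs are the marked visits in Table 8-1 after baseline and up to Week 29 (Day 197). Visits left in P1 = visits up to Week 29 minus 1.

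| Assessment | Post-baseline blinded visits (weeks) | Left in P1 | Last P1 visit | Days before Day 197 |
|---|---|---|---|---|
| Vital signs, haematology, chemistry | 3, 5, 9, 13, 17, 21, 25, 29 | 8 − 1 = 7 | Week 25 (Day 169) | 197 − 169 = 28 |
| ECG | 5, 13, 21, 29 | 4 − 1 = 3 | Week 21 (Day 141) | 197 − 141 = 56 |
| ADA | 3, 13, 29 | 3 − 1 = 2 | Week 13 (Day 85) | 197 − 85 = 112 |
| Coagulation | 13, 29 | 2 − 1 = 1 | Week 13 (Day 85) | 197 − 85 = 112 |

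The coagulation row is conditional. Its post-screening cells carry footnote 6, which is redacted. The same mark sits on the Week 3 and Week 31 doses, which only Cohort 2 receives, so the row probably applies to Cohort 2 alone.

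**Step 3: exposure behind the last P1 value.** Assessments precede dosing at every visit, so a Week 25 value is taken before the Week 25 dose. Under the SAP rule:
- no scheduled P1 vital sign or laboratory value follows the last blinded dose (Week 25);
- no P1 ECG follows the doses at Weeks 21 and 25 (2 doses);
- no P1 ADA sample follows the doses at Weeks 13, 17, 21 and 25 (4 doses).

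**Step 4: where the values go.** SAP section 8.2 summarises vital signs and ECG by period, treatment and visit, and adverse events by period and treatment. Protocol section 12.5.2 asks for all safety tables by period and treatment group. Week 29 therefore becomes the first visit of the open-label period (P2), shown by sequence.

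**Step 5: patients without an open-label dose.** The disposition text in SAP section 8.2 provides for patients who stop treatment before Week 29 dosing, and protocol section 9.1.1 asks such patients to keep attending visits. They can have Week 29 safety data, yet the sequences cover only people in the extension. The SAP gives these patients no P2 group.

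**Step 6: consistency within the SAP.** Disposition is cut at Week 29 dosing, and the PhGA and PGA models in section 7.2.3 use data up to Week 29. Safety alone moves the whole visit.

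**The case against.** The strongest reply is that Visit 190 is a mixed visit. Injection reactions and adverse events that start after the Week 29 dose do belong in P2, and SAP section 8 at least settles the overlap in section 5 explicitly. That stands for post-dose events. It does not justify moving scheduled assessments that precede the dose.

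A reader might infer that placebo values are counted as active-arm data. The documents do not support this: the sequences keep former placebo patients in their own column. The misattribution is to the period, not to the arm.

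A reader might also infer that the Week 29 comparison is lost altogether. It is not. Vital signs and ECG have by-visit rows, laboratory changes are given for each visit and ADA by visit, and the sequences correspond to the randomised arms. By-visit results are moved and mislabelled, not deleted.

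Worst-value shift tables and counts of notable values are less certain. The readable SAP does not say that they are split by period, and part of the laboratory text is redacted. The protocol's general instruction makes a split likely, but it cannot be confirmed.

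SAP section 8 also says that "the “Post-treatment Follow-up” epoch will be summarized together with P2". One might call this a second error, because follow-up varies between patients. However, both documents define the on-treatment period as running to end of study, and drug effects such as B-cell depletion can persist after dosing. Separate or exposure-adjusted follow-up summaries are a preference.

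**Conclusion.** The period rule in SAP section 8 is wrong as written for scheduled Week 29 safety assessments. Its effect is that P1 safety tables end one scheduled assessment early, by the counts in the table above, and that pre-exposure findings in placebo patients fall in the active-drug period wherever results are summarised by period. The overlap in section 5 and the missing P2 group for patients without an open-label dose are part of the same defect.

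This assumes that sites follow the stated order of assessments and dosing, and that tables follow the by-period layout in protocol section 12.5.2. The study is non-confirmatory, safety is descriptive, and the primary endpoint and the PhGA and PGA models are unaffected. It should be fixed, but it does not threaten the trial's main conclusion.

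**What to change.** In SAP section 8:
- Assign scheduled pre-dose Week 29 assessments to P1.
- Assign adverse events and injection reactions by onset relative to the first open-label dose.
- State a convention for adverse events that start on the dosing day without an onset time, for example P2 unless recorded as pre-dose. It is needed because protocol section 10.1.1 asks for start and end dates, not times.
- State that patients with Week 29 data and no open-label dose contribute those data to P1.

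In SAP section 5, remove the Visit 190 overlap for safety, so that the cut matches the Week 29 dosing cut already used for disposition. Separate or exposure-adjusted follow-up summaries are optional.

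The cost is SAP wording and a period-flag derivation, with no new assessments. SAP section 5 says that the final report will cover the VAY736 cohort only, so the change can be made there. CFZ533 results were reported in an earlier interim report, so for that cohort the step is to check which rule those tables used.

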8.1 Variables

Adverse events, vital signs (blood pressure, pulse rate, body temperature), ECG intervals, laboratory measurements, as well as subject demographics, baseline characteristics, and treatment information.

8.2 Descriptive analyses

Subject disposition

The following study disposition data will be listed by treatment and patients will be summarized by treatment by presenting randomized patients who completed the study, discontinued from the study, primary reason for discontinuation from study, patients who discontinued treatment on or before Week 29 (patients who discontinued from treatment before Week 29 dosing), primary reason for discontinuation of treatment on or before week 29, patients who discontinued treatment after Week 29 till EoT (patients who discontinued from treatment after Week 29 dosing till EoT), primary reason for discontinuation of treatment after Week 29 till EoT, discontinuation during the post-treatment follow-up, and primary reason for discontinuation during the post-treatment follow-up periods.

Subject demographics and other baseline characteristics

All data for background and demographic variables will be listed by treatment and patient and summarized by period, treatment.

Relevant medical history, current medical conditions, results of laboratory screens, drug tests and any other relevant information will be listed by treatment and participant.

Treatment

Use of concomitant medications and administration of study drug will be listed by treatment and participant.

Vital signs

All vital signs data will be listed by treatment, participant, and visit and if ranges are available abnormalities (and relevant orthostatic changes) will be flagged. Summary statistics will be provided by period, treatment and visit. Clinically notable changes in vital signs will be summarized.

When repeated assessments are collected in any visit, the average of the values at that visit will be used in the analyses.

ECG evaluations

All ECG data will be listed by treatment, patient and visit, and abnormalities will be flagged. Summary statistics will be provided by period, treatment and visit.

Clinical laboratory evaluations

CCI

Descriptive summary statistics for the change from baseline to each study visit will be presented by test group, and laboratory test.

Shift tables based on the normal laboratory ranges will also be provided. For the shift tables, the normal laboratory ranges will be used to evaluate whether a particular laboratory test value was normal, low, or high for worst post-baseline relative to the baseline. These summaries will be presented by laboratory test category.

The number and percentage of patients with clinically notable laboratory results after baseline will be presented.

Adverse events

All information obtained on adverse events will be displayed by treatment and participant.

The number and percentage of patients with adverse events will be tabulated by body system and preferred term with a breakdown by period and treatment. A patient with multiple adverse events within a body system is only counted once towards the total of this body system and treatment. Separate tables and listings will be presented indicating event severity and study drug relationship.

The on-treatment/ treatment emergent period lasts from date of first administration of study treatment until end of study (EoS). Summary tables for adverse events (AEs) will summarize only on-treatment events, with a start date during the on-treatment period (treatment emergent AEs).

For the legal requirements of ClinicalTrials.gov and EudraCT, two required tables on <on-treatment/treatment emergent> adverse events which are not serious adverse events with an incidence greater than 5% and on <on-treatment/treatment emergent> serious adverse events and SAE suspected to be related to study treatment will be provided by system organ class and preferred term on the safety set population.

If for a same patient, several consecutive AEs (irrespective of study treatment causality, seriousness and severity) occurred with the same SOC and PT:

- a single occurrence will be counted if there is ≤ 1 day gap between the end date of the preceding AE and the start date of the consecutive AE
- more than one occurrence will be counted if there is > 1 day gap between the end date of the preceding AE and the start date of the consecutive AE.

For occurrence, the presence of at least one SAE / SAE suspected to be related to study treatment / non-SAE has to be checked in a block e.g., among AE's in a ≤ 1 day gap block, if at least one SAE is occurring, then one occurrence is calculated for that SAE.

The number of deaths resulting from SAEs suspected to be related to study treatment and SAEs irrespective of study treatment relationship will be provided by SOC and PT.

Injection-related Reactions

Injection-related reactions will be summarized by type of injection reaction (overall, local and systemic), by grading, and by visit. Injection-related reaction events will be listed by treatment, patient and visit/time.

Other safety evaluations

Pregnancy test results will be listed by treatment, patient and visit/time.

[figure not shown]
Immunogenicity

[figure not shown]
The frequency and proportion of ADA-positive patients will be displayed by treatment and visit. Immunogenicity results will be listed by treatment, patient and visit/time.

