After completion of the open-label treatment period, all patients will enter a Follow-Up period in order to monitor safety and efficacy up to Week 69. The Week 69 visit is the End of Study (EoS) visit for patients in Cohort 2 (CFZ533). Study duration for patients in Cohort 2 will be approximately 18 months.

For Cohort 1 (VAY736). Patients who do not achieve B cell recovery by Week 69 Visit will enter into a Secondary Follow-Up period up to 2 years after EoT or until achieving B cell recovery criteria (B cell count is at ≥ 50 cells/ μ l or at least 80% of baseline levels), whichever occurs earlier.

Please also refer to the [Assessment Schedule](#).

4 Rationale

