4.2 Rationale for dose/regimen and duration of treatment

4.2.1 Study treatment duration

The 28 weeks of blinded treatment are considered appropriate to show clinical effects of the study treatments on the underlying SLE disease mechanism. The 5-month open label period, starting at Study Week 29, offers patients on placebo the potential benefit of active treatment. The overall treatment duration of up to 48 weeks will demonstrate effects on disease flare rate and sustainability of clinical effects.

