12.5.2 Safety endpoints

For all safety analyses, the safety set will be used. All listings and tables will be presented by period and treatment group.

Safety summaries (tables, figures) include only data from the on-treatment period with the exception of baseline data which will also be summarized where appropriate (e.g., change from baseline summaries). In addition, a separate summary for death including on treatment and post treatment deaths will be provided. In particular, summary tables for adverse events (AEs) will summarize only on-treatment events, with a start date during the on-treatment period (*treatment-emergent* AEs).

The on-treatment period lasts from the date of first administration of study treatment until end of study (EoS).

Adverse events

All information obtained on adverse events will be displayed by treatment group and subject.

The number (and percentage) of subjects with treatment emergent adverse events (events started after the first dose of study medication or events present prior to start of double-blind treatment but increased in severity based on preferred term) will be summarized in the following ways:

1. by treatment group, primary system organ class and preferred term.
2. by treatment group, primary system organ class, preferred term and maximum severity.

Separate summaries will be provided for study medication related adverse events, death, serious adverse events, other significant adverse events leading to discontinuation and adverse events leading to dose adjustment.

The number (and proportion) of subjects with adverse events of special interest will be summarized by treatment group. A subject with multiple adverse events within a primary system organ class is only counted once towards the total of the primary system organ class.

Vital signs

All vital signs data will be listed by treatment group, subject, and visit and if ranges are available, abnormalities will be flagged. Summary statistics (e.g., change from baseline and shift tables) will be provided by treatment group and visit.

12-lead ECG

All ECG data will be listed by treatment group, subject and visit, abnormalities will be flagged. Summary statistics will be provided by treatment group and visit.

1. PR, QRS, QT, QTcF, and RR intervals will be obtained from 12-lead ECGs for each subject during the study. ECG data will be read and interpreted (/locally).

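### In the VAY736 cohort the post-Week 29 AE tables pool open-label dosing with a follow-up that can last until B cell recovery, yet give only crude percentages with no time at risk

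*SAP*

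**What the plan says.** - **Measure.** SAP 8.2 has the number and percentage of patients with AEs "tabulated by body system and preferred term with a breakdown by period and treatment". Protocol 12.5.2 agrees: "All listings and tables will be presented by period and treatment group".
- **Window.** Under SAP 8.2 the treatment-emergent period "lasts from date of first administration of study treatment until end of study (EoS". Protocol 12.5.2 uses the same window.
- **Periods.** SAP section 5 defines P2 (Visit 190 up to EoT) and P3 (from the day after EoT) as separate periods. The opening paragraph of SAP section 8 then says that, for safety, the post-treatment follow-up "epoch will be summarized together with P2".
- **End of follow-up.** For Cohort 2 it is fixed (Protocol section 3): "The Week 69 visit is the End of Study (EoS) visit for patients in Cohort 2 (CFZ533". For Cohort 1, patients not recovered at Week 69 continue "up to 2 years after EoT or until achieving B cell recovery criteria", whichever is earlier. SAP 1.4 limits that cap: "As per protocol amendment 5 and applicable only for the 3 last patients". For all other patients it states follow-up to recovery with no upper limit. Protocol Table 8-2 lists visits to Week 225.
- **Exposure.** Protocol 12.3 summarises duration of drug exposure. SAP 8.2 only lists study drug administration. Neither gives time at risk, and no exposure-adjusted AE rate appears in the visible text.

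**The concern.** A crude percentage counts anyone with at least one event, so it rises with the length of observation even when risk is unchanged. In the pooled Cohort 1 period, length of observation is decided by how fast B cells return, which is an effect of VAY736. Patients who stay depleted longer are watched longer and can show more events for that reason alone.

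The two columns of that table are VAY736/VAY736 and placebo/VAY736. They differ in scheduled VAY736 doses, so their recovery times may differ. If they do, a gap in AE percentages cannot be separated into more risk and more watching.

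Pooling also hides timing. Protocol 4.5.1 describes late onset neutropenia as arising in the recovery period, more than 16 weeks after treatment, and gives long follow-up as the means of evaluating malignancy. Both would sit in one column with events during dosing. The registry tables with a 5% cut use the same treatment-emergent window. The final CSR covers Cohort 1 only (SAP section 5), the cohort with the variable follow-up.

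**Working it through.** **1. Visit calendar.** Day = 7 × (week − 1) + 1 reproduces the scheduled days in Protocol Tables 8-1 and 8-2: Week 29 = Day 197, Week 53 = Day 365, Week 69 = Day 477, Week 225 = Day 1569.

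**2. Time at risk.** Difference in days ÷ 7, with 2 years taken as 730 days:

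| Patient's last visit | P2 (weeks) | P3 (weeks) | P2 + P3 (weeks) |
|---|---|---|---|
| Week 69 | (365 − 197)/7 = 24 | (477 − 365)/7 = 16 | 40 |
| 2 years after EoT | 24 | 730/7 = 104.3 | 128.3 |
| Week 225 | 24 | (1569 − 365)/7 = 172 | 196 |

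The pooled period can differ between patients by a factor of 128.3/40 = 3.2, or 196/40 = 4.9. All of the variation comes from P3. The blinded period P1 is (197 − 1)/7 = 28 weeks in every arm, as planned in Protocol 4.2.1 ("The 28 weeks of blinded treatment are considered appropriate").

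**3. Scheduled VAY736 doses.** Every 4 weeks from Week 1 to Week 49: (49 − 1)/4 + 1 = 13. From Week 29 to Week 49: (49 − 29)/4 + 1 = 6.

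**4. What this can do to the two sequences.** The documents give neither an event rate nor the share of each sequence that needs secondary follow-up, so both are assumed here. With constant rate λ per patient-year, crude incidence over d days is 1 − exp(−λd/365.25). Over P2 + P3, d = 280 to Week 69 and d = 898 to the cap:

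- λ = 0.1: 7.4% and 21.8%
- λ = 0.2: 14.2% and 38.8%

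Let a share s of a sequence stay to the cap and the rest stop at Week 69. The expected percentage is s × (value at cap) + (1 − s) × (value at Week 69).

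| Shares to cap | Mean weeks | λ = 0.1 | λ = 0.2 |
|---|---|---|---|
| 50% v 50% | 84.1 v 84.1 | 14.6% v 14.6% | 26.5% v 26.5% |
| 60% v 40% | 93.0 v 75.3 | 16.0% v 13.1% | 29.0% v 24.1% |
| 80% v 40% | 110.6 v 75.3 | 18.9% v 13.1% | 33.9% v 24.1% |

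For example, at λ = 0.2: 0.6 × 38.8 + 0.4 × 14.2 = 29.0, and 0.4 × 38.8 + 0.6 × 14.2 = 24.0 (24.1 before rounding). With a 52-week year and 128 weeks, the 13.1% becomes 13.2%.

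**5. Same scenario as a rate.** With time stopped at first event and a constant hazard, expected time at risk per patient is (expected proportion)/λ. For 60% v 40% at λ = 0.2 this is 0.290/0.2 = 1.45 years and 0.241/0.2 = 1.20 years. The rates are 0.290/1.45 = 0.20 and 0.241/1.20 = 0.20, so the artificial gap disappears.

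**The case against.** The strongest reply is that nothing comparative is damaged. Tables are split by period, so the randomised active v placebo comparison keeps its equal planned 28 weeks. Cohorts are analysed separately, so Cohort 2's fixed end at Week 69 creates no planned comparison with Cohort 1. Both stand.

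A reader might infer that the two Cohort 1 sequences have very unequal time at risk. The documents do not support that. Both sequences take VAY736 from Week 29 under the same follow-up rule, and nothing visible says how many in either entered secondary follow-up or for how long. The 13 v 6 doses make a difference plausible, not established. Setting 7.4% against 21.8% compares patients at opposite ends of the range, not groups. Week 225 is a listed visit; no text says anyone reached it.

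The gaps may also be small. At about 30 per arm (Protocol 12.8.1), 16.0% v 13.1% is 0.029 × 30 = 0.9 of a patient, and 29.0% v 24.1% is 0.049 × 30 = 1.5. A constant hazard does not suit injection reactions, which follow dosing and, for systemic reactions, mostly the first dose (Protocol 4.5.1). Extra off-treatment time adds little to them.

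The long window is deliberate and defensible, because depletion can last for months or years. Table shells sit in a separate document and parts of the SAP are blacked out, so an adjusted analysis may exist elsewhere. None of this supplies a time denominator in the visible AE plan, nor a reason to undo the split that SAP section 5 makes.

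**Conclusion.** The point holds as a reporting weakness confined to Cohort 1 after Week 29. The pooling rule, the crude percentages and the recovery-dependent end of follow-up are all stated in the documents. The range of 40 to 128 or 196 weeks per patient follows from the visit calendar.

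The effect on the comparison between sequences is conditional. It is zero if equal shares need the same follow-up. It is about 3 percentage points at 0.1 events per patient-year and about 5 at 0.2, if 60% v 40% stay to the cap. These figures rest on assumed rates, assumed shares and a constant hazard. They apply to events that accrue with time, such as infection, late neutropenia and malignancy. The study is non-confirmatory and its safety tables are descriptive, so no inferential result changes. The correction is still worth making, because without a time denominator those percentages cannot be interpreted.

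**What to change.** In SAP section 8, drop the rule that summarises P3 with P2. Tabulate AEs for P2 (Week 29 dose to EoT) and P3 separately, as section 5 defines them.

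In SAP 8.2, show patient-years at risk and the exposure-adjusted incidence rate beside each number and percentage: patients with an event per 100 patient-years, with time stopped at the first event. The split alone is not enough. It gives P2 a common planned 24 weeks, but P3 still runs from 16 weeks upward. Keep the collection window to EoS.

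A supplementary table cut at Week 69 would give every completer the same 40 weeks.

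The cost is extra columns in the AE tables. AE, dosing and visit dates are already collected, so no new data are needed. The rates assume a roughly constant hazard within each period, which should be stated in a footnote; they are of little use for injection reactions.
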